Missing		xxx	xxx	xxx	xxx	xxx	xxx		
n	Change	xxx	xxx	xxx	xxx	xxx	xxx		
Mean (SD)		xx.x (x.xx)	xx.x (x.xx)	xx.x (x.xx)	xx.x (x.xx)	xx.x (x.xx)	xx.x (x.xx)		
Median		xx.x	xx.x	xx.x	xx.x	xx.x	xx.x		
Min, Max		xx, xx	xx, xx	xx, xx	xx, xx	xx, xx	xx, xx		
Missing		xxx	xxx	xxx	xxx	xxx	xxx		
. . .									

Note: Percentages are based on the number of patients in each cumulative dose group.

Trevena, Inc.
Protocol CP130-3003

CONFIDENTIAL
Page x of y

- [a] See section 6.2.3 of the SAP for windowed time point intervals.
- [b] Baseline is the last non-missing value prior to the patient receiving the first dose of oliceridine.
- [c] Only patients with both a baseline value and a windowed time point value are summarized at a given windowed time point.

Programmer's Note: Repeat Parameter (unit) in each page if it wraps on to multiple pages.

Table 14.3.7.1.1
Selected QTcF Thresholds
(Safety Analysis Set)

Windowed Time Point [a]	Oliceridine <= 4 mg N=XXX n (%)	Oliceridine >4 to 8 mg N=XXX n (%)	Oliceridine >8 to 16 mg N=XXX n (%)	Oliceridine >16 to 36 mg N=XXX n (%)	Oliceridine >36 mg N=XXX n (%)	All Treated Patients N=XXX n (%)
Overall	xxx	xxx	xxx	xxx	xxx	xxx
Change from Baseline of > 30 msec	xxx (xxx.x)	xxx (xxx.x)	xxx (xxx.x)	xxx (xxx.x)	xxx (xxx.x)	xxx (xxx.x)
Change from Baseline of > 60 msec	xxx (xxx.x)	xxx (xxx.x)	xxx (xxx.x)	xxx (xxx.x)	xxx (xxx.x)	xxx (xxx.x)
Increase to > 500 msec	xxx (xxx.x)	xxx (xxx.x)	xxx (xxx.x)	xxx (xxx.x)	xxx (xxx.x)	xxx (xxx.x)
<T30 Minutes>	xxx	xxx	xxx	xxx	xxx	xxx
Change from Baseline of > 30 msec	xxx (xxx.x)	xxx (xxx.x)	xxx (xxx.x)	xxx (xxx.x)	xxx (xxx.x)	xxx (xxx.x)
Change from Baseline of > 60 msec	xxx (xxx.x)	xxx (xxx.x)	xxx (xxx.x)	xxx (xxx.x)	xxx (xxx.x)	xxx (xxx.x)
Increase to > 500 msec	xxx (xxx.x)	xxx (xxx.x)	xxx (xxx.x)	xxx (xxx.x)	xxx (xxx.x)	xxx (xxx.x)
...						

Note: Percentages are based on the number of patients in each cumulative dose group.

Baseline is the last non-missing value prior to the patient receiving the first dose of oliceridine.

[a] See section 6.2.3 of the SAP for windowed time point intervals.

Programmer's Note: Display all ECG windowed time points after overall.

Table 14.3.7.1.2
Summary of Electrocardiogram (ECG) Findings
(Safety Analysis Set)

Windowed Time Point [a] Finding	Oliceridine <= 4 mg N=XXX n (%)	Oliceridine >4 to 8 mg N=XXX n (%)	Oliceridine >8 to 16 mg N=XXX n (%)	Oliceridine >16 to 36 mg N=XXX n (%)	Oliceridine >36 mg N=XXX n (%)	All Treated Patients N=XXX n (%)
Patients with at Least 1 Clinically Significant ECG Result	xxx (xxx.x)	xxx (xxx.x)	xxx (xxx.x)	xxx (xxx.x)	xxx (xxx.x)	xxx (xxx.x)
Baseline [b]						
Normal	xxx (xxx.x)	xxx (xxx.x)	xxx (xxx.x)	xxx (xxx.x)	xxx (xxx.x)	xxx (xxx.x)
Abnormal, NCS	xxx (xxx.x)	xxx (xxx.x)	xxx (xxx.x)	xxx (xxx.x)	xxx (xxx.x)	xxx (xxx.x)
Abnormal, CSig	xxx (xxx.x)	xxx (xxx.x)	xxx (xxx.x)	xxx (xxx.x)	xxx (xxx.x)	xxx (xxx.x)
Missing	xxx (xxx.x)	xxx (xxx.x)	xxx (xxx.x)	xxx (xxx.x)	xxx (xxx.x)	xxx (xxx.x)
<T30 Minutes>						
Normal	xxx (xxx.x)	xxx (xxx.x)	xxx (xxx.x)	xxx (xxx.x)	xxx (xxx.x)	xxx (xxx.x)
Abnormal, NCS	xxx (xxx.x)	xxx (xxx.x)	xxx (xxx.x)	xxx (xxx.x)	xxx (xxx.x)	xxx (xxx.x)
Abnormal, CSig	xxx (xxx.x)	xxx (xxx.x)	xxx (xxx.x)	xxx (xxx.x)	xxx (xxx.x)	xxx (xxx.x)
Missing	xxx (xxx.x)	xxx (xxx.x)	xxx (xxx.x)	xxx (xxx.x)	xxx (xxx.x)	xxx (xxx.x)
...						

Note: NCS = Not clinically significant; CSig = Clinically significant.

Clinical significance is based on the investigator interpretation as recorded.

Percentages are based on the number of patients in each cumulative dose group.

[a] See section 6.2.3 of the SAP for windowed time point intervals.

[b] Baseline is the last non-missing value prior to the patient receiving the first dose of oliceridine.

Table 14.3.8.1
Summary of Subjective Opioid Withdrawal Scale (SOWS) Total Score
(Safety Analysis Set)

	Oliceridine <= 4 mg N=XXX	Oliceridine >4 to 8 mg N=XXX	Oliceridine >8 to 16 mg N=XXX	Oliceridine >16 to 36 mg N=XXX	Oliceridine >36 mg N=XXX	All Treated Patients N=XXX
N	xxx	xxx	xxx	xxx	xxx	xxx
Mean (SD)	xx.x (x.xx)	xx.x (x.xx)	xx.x (x.xx)	xx.x (x.xx)	xx.x (x.xx)	xx.x (x.xx)
Median	xx.x	xx.x	xx.x	xx.x	xx.x	xx.x
Min, Max	xx, xx	xx, xx	xx, xx	xx, xx	xx, xx	xx, xx
Missing	xxx	xxx	xxx	xxx	xxx	xxx

Note: Total score is derived by summing the individual symptom intensities. If no more than half of the symptoms are missing, imputation with the mean score of the non-missing questions is used to calculate total score. If more than half of the symptoms are missing the total score is also set to missing.

Trevena, Inc.
Protocol CP130-3003CONFIDENTIAL
Page x of yTable 14.3.9.1
Summary of Plasma Concentrations
(Safety Analysis Set)

Windowed Time Point [a]	Oliceridine <= 4 mg N=XXX	Oliceridine >4 to 8 mg N=XXX	Oliceridine >8 to 16 mg N=XXX	Oliceridine >16 to 36 mg N=XXX	Oliceridine >36 mg N=XXX	All Treated Patients N=XXX
T30 Minutes						
N	xxx	xxx	xxx	xxx	xxx	xxx
Mean (SD)	xx.x (x.xx)	xx.x (x.xx)	xx.x (x.xx)	xx.x (x.xx)	xx.x (x.xx)	xx.x (x.xx)
Median	xx.x	xx.x	xx.x	xx.x	xx.x	xx.x
Min, Max	xx, xx	xx, xx	xx, xx	xx, xx	xx, xx	xx, xx
Missing	xxx	xxx	xxx	xxx	xxx	xxx
T1.5 Hours						
N	xxx	xxx	xxx	xxx	xxx	xxx
Mean (SD)	xx.x (x.xx)	xx.x (x.xx)	xx.x (x.xx)	xx.x (x.xx)	xx.x (x.xx)	xx.x (x.xx)
Median	xx.x	xx.x	xx.x	xx.x	xx.x	xx.x
Min, Max	xx, xx	xx, xx	xx, xx	xx, xx	xx, xx	xx, xx
Missing	xxx	xxx	xxx	xxx	xxx	xxx

Note: Unscheduled PK samples will be displayed in the listing.

[a] See section 6.2.3 of the SAP for windowed time point intervals.

Trevena, Inc.
Protocol CP130-3003

CONFIDENTIAL
Page x of y

Listing 16.2.1.1
Patient Disposition
(Enrolled Analysis Set)

Patient ID	Sex/Age/ Cumulative Dose Group	Date/Time of First Dose of Oliceridine	Date/Time of End of Treatment (Cumulative Duration of Exposure [b])	Date of Study Completion/ Discontinuation[a]	Primary Reason for Termination (Other)

[a] Date/time of study completion/discontinuation is the date collected at the end of study instead of the of the date/time last dose received.

[b] Duration is defined as the difference in total hours from the first dose to the last dose of study medication.

Trevena, Inc.
Protocol CP130-3003

CONFIDENTIAL
Page x of y

Listing 16.2.1.2
Inclusion/Exclusion Criteria
(Enrolled Analysis Set)

Patient ID	Sex/Age/ Cumulative Dose Group	Met all Eligibility Criteria?	Criteria not Met
------------	-----------------------------------	-------------------------------	------------------

Note: Patients may fail screening for more than one reason.

Trevena, Inc.
Protocol CP130-3003

CONFIDENTIAL
Page x of y

Listing 16.2.1.3
Protocol Deviations
(Enrolled Analysis Set)

Cumulative Dose Group: Oliceridine <= 4 mg

Patient ID/Sex/Age	Deviation Type	Deviation Text Detail	Deviation Criticality	IRB Reportable?/Report Date
--------------------	----------------	-----------------------	-----------------------	-----------------------------

Note: IRB = Institutional Review Board.

Trevena, Inc.
Protocol CP130-3003CONFIDENTIAL
Page x of yListing 16.2.2.1
Demographics and Baseline Characteristics
(Enrolled Analysis Set)

Cumulative Dose Group: Oliceridine <= 4 mg

Patient ID/Sex/Age	Race/ Specify Ethnicity	Informed Consent Date	Baseline Height (cm)/ Weight (kg)/ BMI (kg/m ²)	ASA Physical Status Classification [a]	ESI Classification	CYP2D6 Phenotype (EM vs PM)

Note: BMI = Body mass index; ASA = American Society of Anesthesiologists; ESI = Emergency Severity Index;
EM = Extensive metabolizer; PM = Poor metabolizer.

- [a] ASA Physical Status is defined as follows: I - Normal healthy patient; II - Patient with mild systemic disease; III - Patient with severe systemic disease; IV - Patient with severe systemic disease that is a constant threat to life; V - Moribund patient who is not expected to survive without the operation; VI - Declared brain-dead patient whose organs are being removed for donor purposes.
- [b] Extensive Metabolizer patients include those with a predictive phenotype of Ultra Metabolizer or Extensive Metabolizer; Poor Metabolizer patients include those with a predictive phenotype of Intermediate Metabolizer or Poor Metabolizer.

Trevena, Inc.
Protocol CP130-3003CONFIDENTIAL
Page x of yListing 16.2.2.2
Prior and Concomitant Medications
(Enrolled Analysis Set)

Cumulative Dose Group: Oliceridine <= 4 mg

Patient ID/Sex/Age	Base Preferred Name/ ATC Class/ Medication	Start Date/Time	Stop Date/Time or Ongoing	Dose and P/C Unit	Route (Other)	Frequency	Indication	Given for AE?/ AE #
--------------------	--	-----------------	------------------------------	----------------------	---------------	-----------	------------	------------------------

Note: AE = Adverse Event; ATC = Anatomic Therapeutic Chemical; P = Prior Medication; C = Concomitant Medication;

Programmer's Note: Sort by Start date/time. For missing date/times sort alphabetically

Trevena, Inc.
Protocol CP130-3003

CONFIDENTIAL
Page x of y

Listing 16.2.2.3
Reason for Receiving Oliceridine
(Safety Analysis Set)

Cumulative Dose Group: Oliceridine <= 4 mg

Patient ID/Sex/Age	Initial Setting	Condition	ICD-10 Code/ICD Description	Specialty
--------------------	-----------------	-----------	-----------------------------	-----------

Trevena, Inc.
Protocol CP130-3003

CONFIDENTIAL
Page x of y

Listing 16.2.2.4
Medical History
(Enrolled Analysis Set)

Patient ID	Sex/Age/ Cumulative Dose Group	Medical History	System Organ Class	Preferred Term	Start Date	Stop Date or Ongoing
------------	--------------------------------------	--------------------	-----------------------	----------------	------------	-------------------------

Trevena, Inc.
Protocol CP130-3003

CONFIDENTIAL
Page x of y

Listing 16.2.3.1
Study Drug Administration
(Safety Analysis Set)

Cumulative Dose Group: Oliceridine <= 4 mg

Patient ID/Sex/Age	Method of Administration	Start Date/Time	Windowed Time Point [a]	Dose Received	Cumulative Dose

Note: Asterisk (*) denotes the last dose received.

[a] See section 6.2.3 of the SAP for windowed time point intervals.

Trevena, Inc.
Protocol CP130-3003

CONFIDENTIAL
Page x of y

Listing 16.2.4.1
Numeric Pain Rating Scale (NPRS) Scores
(Safety Analysis Set)

Cumulative Dose Group: Oliceridine <= 4 mg

Patient ID/Sex/Age	Assessment Date/Time	Windowed Time Point[a]	Numeric Pain Rating Scale (NPRS) Score
--------------------	----------------------	------------------------	--

Note: Asterisk (*) denotes the value used in descriptive summary statistics.

[a] See section 6.2.3 of the SAP for windowed time point intervals.

Trevena, Inc.
Protocol CP130-3003

CONFIDENTIAL
Page x of y

Listing 16.2.5.1
Adverse Events
(Enrolled Analysis Set)

Patient ID/Sex/Age/Cumulative Dose Group: 1001/Male/30/ Oliceridine <= 4 mg

System Organ Class/ Preferred Term [a]/ Verbatim Term	Start Date/Time/ End Date/Time AE #	Concomitant Intensity/ Relationship	medication given?/CM #	Action Taken	Serious?/ Outcome	Reason for Serious	Additional Information
---	--	---	---------------------------	-----------------	----------------------	--------------------	---------------------------

Note: All adverse events were coded using MedDRA version 19.0. TEAEs are defined in section 6.3.3 of the SAP.

Trevena, Inc.
Protocol CP130-3003

CONFIDENTIAL
Page x of y

Listing 16.2.6.1
Vital Signs
(Safety Analysis Set)

Cumulative Dose Group: Oliceridine <= 4 mg

Patient ID/Sex/Age	Collection Date/Time	Windowed Time Point [a]	Systolic Blood Pressure (mmHg)	Diastolic Blood Pressure (mmHg)	Heart Rate (beats/min)	Respiratory Rate (breaths/min)	Oral Temperature (C)	Pulse Oximetry (SpO2 %)
--------------------	----------------------	-------------------------	--------------------------------	---------------------------------	------------------------	--------------------------------	----------------------	-------------------------

Note: Asterisk (*) denotes the value used in descriptive summary statistics.

[a] See section 6.2.3 of the SAP for windowed time point intervals.

Trevena, Inc.
Protocol CP130-3003

CONFIDENTIAL
Page x of y

Listing 16.2.7.1
Laboratory Results: Chemistry
(Safety Analysis Set)

Cumulative Dose Group: Oliceridine <= 4 mg

Patient ID/Sex/Age	Lab Collection Date/Time	Windowed Time Point [a]	Lab Test (Unit)	Lab Value	Overall Interpretation
--------------------	--------------------------	-------------------------	-----------------	-----------	------------------------

Note: N = Normal; NCS = Not Clinically Significant; Csig = Clinically Significant;
Asterisk (*) denotes the value used in descriptive summary statistics.
The investigator will exercise his or her medical and scientific judgement in deciding whether an abnormal laboratory finding is clinically significant.

[a] See section 6.2.3 of the SAP for windowed time point intervals.

Trevena, Inc.
Protocol CP130-3003

CONFIDENTIAL
Page x of y

Use the same template as for Listing 16.2.7.1 for the following listings:

Listing 16.2.7.2
Laboratory Results: Hematology
(Safety Analysis Set)

Trevena, Inc.
Protocol CP130-3003CONFIDENTIAL
Page x of yListing 16.2.8
12 Lead Electrocardiogram Results
(Safety Analysis Set)

Patient ID/Sex/Age/Cumulative Dose Group: 1001/Male/30/ Oliceridine <= 4 mg

Assessment Date/Time	Windowed Time Point[a]			RR	QRS	QT	QTcF	Interpreta tion	Abnormal, Sepcify
		Heart Rate (beats/min)	PR Interval (msec)	Interval (msec)	Interval (msec)	Interval (msec)			

Note: Csig = Clinically Significant; NCS = Not Clinically Significant.

Asterisk (*) denotes the value used in descriptive summary statistics.

Trevena, Inc.
Protocol CP130-3003

CONFIDENTIAL
Page x of y

Listing 16.2.9
Subjective Opioid Withdrawal Scale (SOWS)
(Safety Analysis Set)

Cumulative Dose Group: Oliceridine <= 4 mg

Patient ID/Sex/Age	Assessment Date/Time	Symptom	Intensity Rating [a]
--------------------	----------------------	---------	----------------------

[a] 0 = Not at all; 1 = A little; 2 = Moderately; 3 = Quite a bit; 4 = Extremely.

Trevena, Inc.
Protocol CP130-3003

CONFIDENTIAL
Page x of y

Listing 16.2.10
Physical Examination
(Safety Analysis Set)

Cumulative Dose Group: Oliceridine <= 4 mg

Patient ID/Sex/Age

Assessment Date/Time

Changes From Previous Visit?

Trevena, Inc.
Protocol CP130-3003

CONFIDENTIAL
Page x of y

Listing 16.2.11
Moline-Roberts Pharmacologic Sedation Scale Score
(Safety Analysis Set)

Cumulative Dose Group: Oliceridine <= 4 mg

Patient ID/Sex/Age	Assessment Date/Time	Windowed Time Point [a]	Total Score
--------------------	----------------------	-------------------------	-------------

Note: Asterisk (*) denotes the value used in descriptive summary statistics.

[a] See section 6.2.3 of the SAP for windowed time point intervals.

Trevena, Inc.
Protocol CP130-3003CONFIDENTIAL
Page x of yListing 16.2.12.x
Patient Profiles for Patients with Durations Over 96 Hours
(Safety Analysis Set)

Patient ID/Sex/Age/Cumulative Dose Group: *****

Method of Administration	Cumulative Oliceridine Dose (mg)	Cumulative Duration of Exposure [a] (Hours)	Completed the Study? [b]	Reason for Early Termination
xx	xx	xx		

Base Preferred Name/ ATC Class/ Medication	Start Date/ Time	Stop Date/ Time or Ongoing	P/C	Dose and Unit	Route (Other)	Frequency	Indication	Given for AE?/ AE #

[figure not shown]
System Organ Class/ Preferred Term [a]/ Verbatim Term	AE #	Start Date/ Time/ End Date/ Time (or Ongoing)	Intensity/ Relationship	Action Taken	Outcome	Serious?/ Reason for Seriousness

Note: AE = Adverse Event; ATC = Anatomic Therapeutic Chemical; P = Prior Medication; C = Concomitant Medication;

All adverse events were coded using MedDRA version 19.0.

[a] Duration is defined as the difference in total hours from the first dose to the last dose of study medication.

[figure not shown]
[b] Because the duration of treatment for each patient in this study will be determined by the clinical need for parenteral opioid therapy, a patient will be considered to be a completer if no early termination reason is indicated.

Figure 1.1
Duration of Treatment by Site
(Safety Analysis Set)

[a] Duration is defined as the difference in total hours from the start of the first dose of study medication to end-time for the last dose of study drug administration.

[figure not shown]
Programmer's Note: Limit to 10 sites per page.

Figure 1.2
Cumulative Dose by Site
(Safety Analysis Set)

Programmer's Note: Limit to 10 sites per page.

Figure 2.1
Cumulative Dose by Duration of Treatment
(Safety Analysis Set)

Note: Each dot in the graph represents a patient.

[a] Duration is defined as the difference in total hours from the start of the first dose of study medication to end-time for the last dose of study drug administration.

Trevena, Inc.
Protocol CP130-3003

CONFIDENTIAL
Page x of y

Use the same template as for Figure 2.1 for the following Figures:

Figure 2.1.1
Cumulative Dose by Duration of Treatment for Patients With at Least 1 TEAE
(Safety Analysis Set)

Figure 2.1.2
Cumulative Dose by Duration of Treatment for Patients With at Least 1 Related TEAE
(Safety Analysis Set)

Figure 2.1.3
Cumulative Dose by Duration of Treatment for Patients With at Least 1 TEAE Leading to Early Discontinuation
(Safety Analysis Set)

Figure 2.1.4
Cumulative Dose by Duration of Treatment for Patients With at Least 1 SAE
(Safety Analysis Set)

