9.3 ASA Physical Status Classification System³

ASA PHYSICAL STATUS CLASSIFICATION SYSTEM

Last approved by the ASA House of Delegates on October 15, 2014

[figure not shown]
Current definitions (NO CHANGE) and Examples (NEW)

ASA PS Classification	Definition	Examples, including, but not limited to:
ASA I	A normal healthy patient	Healthy, non-smoking, no or minimal alcohol use
ASA II	A patient with mild systemic disease	Mild diseases only without substantive functional limitations. Examples include (but not limited to): current smoker, social alcohol drinker, pregnancy, obesity (30 < BMI < 40), well-controlled DM/HTN, mild lung disease
ASA III	A patient with severe systemic disease	Substantive functional limitations; One or more moderate to severe diseases. Examples include (but not limited to): poorly controlled DM or HTN, COPD, morbid obesity (BMI ≥40), active hepatitis, alcohol dependence or abuse, implanted pacemaker, moderate reduction of ejection fraction, ESRD undergoing regularly scheduled dialysis, premature infant PCA <60 weeks, history (>3 months) of MI, CVA, TIA, or CAD/stents.
ASA IV	A patient with severe systemic disease that is a constant threat to life	Examples include (but not limited to): recent (< 3 months) MI, CVA, TIA, or CAD/stents, ongoing cardiac ischemia or severe valve dysfunction, severe reduction of ejection fraction, sepsis, DIC, ARD or ESRD not undergoing regularly scheduled dialysis
ASA V	A moribund patient who is not expected to survive without the operation	Examples include (but not limited to): ruptured abdominal/thoracic aneurysm, massive trauma, intracranial bleed with mass effect, ischemic bowel in the face of significant cardiac pathology or multiple organ/system dysfunction
ASA VI	A declared brain-dead patient whose organs are being removed for donor purposes	

* The addition of "E" denotes Emergency surgery: (An emergency is defined as existing when delay in treatment of the patient would lead to a significant increase in the threat to life or body part)

³ American Society of Anesthesiologists, 2014

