7.7 Examination of Subgroups

The analysis of safety will be examined by looking at the following subgroups: sex (females vs. males); age grouping 1 (<65 years vs. ≥ 65 years); age grouping 2 (≥ 18 to $<$ study median years of safety analysis set population vs. \geq study median years of safety analysis set population); race (white vs non-white); median baseline NPRS score ($<$ median vs. \geq median); initial setting, BMI (<25 vs. ≥ 25), and CYP2D6 metabolizer status.

No statistical testing will be performed for the subgroup analyses but any differences in treatment effect noticed in subgroups may be explored.

Chiltern, International – Confidential

Client: Trevena, Inc.
Version #: 1.0
Version Date: 20Dec2016

Protocol/CIP #: CP130-3003

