8.6.3. Adverse Events

The MedDRA version 19.0 will be used to classify all verbatim AE terms with respect to SOC and PT. Summaries will include only TEAEs and will be summarized for the Safety Analysis Set for each cumulative dose group and for all groups combined.

An overall summary of TEAEs will be performed with the following categories: any TEAE, serious TEAEs, TEAEs with the outcome of fatal, and TEAEs leading to early discontinuation. Severity rating and relationship to study medication categories will also be summarized. The summary will include unique patient counts and percentages based on the number of patients in the cumulative dose group, and the total event count. Overall summary of TEAEs will be repeated by sex, age grouping 1, age grouping 2, race, median baseline NPRS score, BMI, CYP2D6 metabolizer status and initial setting subgroups.

The number and percentage of patients with TEAEs for each cumulative dose group and overall will also be displayed by SOC and PT and will be repeated by BMI and CYP2D6 metabolizer status subgroups. These 3 summary tables will also be repeated for serious TEAEs and TEAEs leading to early discontinuation.

TEAEs will also be summarized by PT only. This summary table will be repeated by BMI and CYP2D6 metabolizer status subgroups.

TEAEs, serious TEAEs and TEAEs resulting in early discontinuation will be summarized by cumulative dose and cumulative time based on the time point intervals defined in section 6.2.4. TEAEs by cumulative dose and cumulative time based on the time point intervals will also be summarized by PTs.

A summary of most common TEAEs will be presented, where PTs occurring in at least 5% of the all treated patients group will be included. Summaries will be sorted by PT in descending frequency in the all treated patients column.

Summaries of TEAEs by maximum severity (mild, moderate, or severe) will be performed by SOC and PT. Patients with missing severities will be counted as severe. Summaries of TEAEs by maximum relationship will be performed by SOC and PT. Patients with missing relationship will be counted as probably related.

The denominator for percentages will be the number of patient within the cumulative dose group for the Safety Analysis Set. The total number of events will be presented

Client: Trevena, Inc.
Version #: 1.0
Version Date: 20Dec2016

Protocol/CIP #: CP130-3003

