11. APPENDICES

11.1 APPENDIX 1: VARIABLE DEFINITIONS

Age will be calculated as the informed consent date minus the date of birth divided by 365.25 [Age=(ICF Date-DOB)/365.25].

Body mass index (BMI; kg/m²) is calculated as: weight (kg) / [height (m)]², rounded to one decimal place.

Chiltern, International – Confidential

Client: Trevena, Inc.
Version #: 1.0
Version Date: 20Dec2016

Protocol/CIP #: CP130-3003

Height and weight are collected in imperial units and will be converted using the following conversion factors:

Height (cm) = height (inches) x 2.54

Weight (kg) = weight (lb) x 0.454

Temperature is collected in degrees Fahrenheit and will be converted to degrees Celcius using the following formula:

$$\text{Temp } (\text{°C}) = [\text{temp } (\text{°F}) - 32] \times \frac{5}{9}$$

Protocol Number CP130-3003

A phase 3, multicenter, open-label study to evaluate the safety of oliceridine (TRV130) in patients with acute pain for which parenteral opioid therapy is warranted

**Mock Data Displays
Final Version 1.0
Date: 20Dec 2016**

Prepared for:
Trevena, Inc.
[name]
[name]

Prepared by:
Chiltern International, Inc.
[name]
[name]

This document is confidential information of Trevena. It may not be disclosed to parties not associated with the clinical investigation or used for any purpose without the prior written consent of Trevena.

Trevena, Inc.
 Protocol CP130-3003
 Mock Data Displays

Table 14.1.1 Protocol Deviation (Safety Analysis Set)	6
Table 14.1.2.1 Patient Population (Enrolled Analysis Set).....	8
Table 14.1.2.2 Summary of Safety Analysis Set (Safety Analysis Set).....	9
Table 14.1.2.3 Summary of Reasons for Screen Failure (Enrolled Analysis Set).....	10
Table 14.1.3 Summary of Reasons for Receiving Oliceridine (Safety Analysis Set).....	11
Table 14.1.4 Medical History by Body System and Medical Condition (Safety Analysis Set)	12
Table 14.1.5 Summary of Patient Disposition (Safety Analysis Set)	13
Table 14.1.6 Demographic and Baseline Characteristics (Safety Analysis Set).....	14
Table 14.1.7 Summary of Prior Medications by Drug Class and Medication (Safety Analysis Set)	18
Table 14.1.8 Summary of Concomitant Medications by Drug Class and Medication (Safety Analysis Set).....	19
Table 14.2.1 Summary of Numeric Pain Rating Scale Change From Baseline (Efficacy Analysis Set)....	20
Table 14.3.1.1 Exposure to Study Drug (Safety Analysis Set).....	21

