[a] Extensive Metabolizer = Normal functional levels of CYP2D6 in the liver. Poor Metabolizer = Low functional levels of CYP2D6 in the liver.

Table 14.1.6 (continued)
Demographic and Baseline Characteristics
(Safety Analysis Set)

Characteristic	Oliceridine <= 4 mg N=XXX	Oliceridine >4 to 8 mg N=XXX	Oliceridine >8 to 16 mg N=XXX	Oliceridine >16 to 36 mg N=XXX	Oliceridine >36 mg N=XXX	All Treated Patients N=XXX
Height (cm)						
N	xxx	xxx	xxx	xxx	xxx	xxx
Mean (SD)	xx.x (x.xx)	xx.x (x.xx)	xx.x (x.xx)	xx.x (x.xx)	xx.x (x.xx)	xx.x (x.xx)
Median	xx.x	xx.x	xx.x	xx.x	xx.x	xx.x
Min, Max	xx, xx	xx, xx	xx, xx	xx, xx	xx, xx	xx, xx
Missing	xxx	xxx	xxx	xxx	xxx	xxx
Weight (kg)						
N	xxx	xxx	xxx	xxx	xxx	xxx
Mean (SD)	xx.x (x.xx)	xx.x (x.xx)	xx.x (x.xx)	xx.x (x.xx)	xx.x (x.xx)	xx.x (x.xx)
Median	xx.x	xx.x	xx.x	xx.x	xx.x	xx.x
Min, Max	xx, xx	xx, xx	xx, xx	xx, xx	xx, xx	xx, xx
Missing	xxx	xxx	xxx	xxx	xxx	xxx
BMI (kg/m**2)						
N	xxx	xxx	xxx	xxx	xxx	xxx
Mean (SD)	xx.x (x.xx)	xx.x (x.xx)	xx.x (x.xx)	xx.x (x.xx)	xx.x (x.xx)	xx.x (x.xx)
Median	xx.x	xx.x	xx.x	xx.x	xx.x	xx.x
Min, Max	xx, xx	xx, xx	xx, xx	xx, xx	xx, xx	xx, xx
Missing	xxx	xxx	xxx	xxx	xxx	xxx
BMI Group (kg/m**2), n (%)						
< 25	xxx (xxx.x)	xxx (xxx.x)	xxx (xxx.x)	xxx (xxx.x)	xxx (xxx.x)	xxx (xxx.x)
>= 25	xxx (xxx.x)	xxx (xxx.x)	xxx (xxx.x)	xxx (xxx.x)	xxx (xxx.x)	xxx (xxx.x)
Missing	xxx (xxx.x)	xxx (xxx.x)	xxx (xxx.x)	xxx (xxx.x)	xxx (xxx.x)	xxx (xxx.x)

Note: Percentages are based on the total number of non-missing values in each cumulative dose group.

[a] Extensive Metabolizer = Normal functional levels of CYP2D6 in the liver. Poor Metabolizer = Low functional levels of CYP2D6 in the liver.

Trevena, Inc.
Protocol CP130-3003CONFIDENTIAL
Page x of yTable 14.1.6 (continued)
Demographic and Baseline Characteristics
(Safety Analysis Set)

Characteristic	Oliceridine <= 4 mg N=XXX	Oliceridine >4 to 8 mg N=XXX	Oliceridine >8 to 16 mg N=XXX	Oliceridine >16 to 36 mg N=XXX	Oliceridine >36 mg N=XXX	All Treated Patients N=XXX
Baseline Pain Intensity						
N	xxx	xxx	xxx	xxx	xxx	xxx
Mean (SD)	xx.x (x.xx)	xx.x (x.xx)	xx.x (x.xx)	xx.x (x.xx)	xx.x (x.xx)	xx.x (x.xx)
Median	xx.x	xx.x	xx.x	xx.x	xx.x	xx.x
Min, Max	xx, xx	xx, xx	xx, xx	xx, xx	xx, xx	xx, xx
Missing	xxx	xxx	xxx	xxx	xxx	xxx

Note: Percentages are based on the total number of non-missing values in each cumulative dose group.

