Patients are counted once within each system organ class and each preferred term.

TEAEs are defined in section 6.3.3 of the SAP.

Trevena, Inc.
Protocol CP130-3003

CONFIDENTIAL
Page x of y

Use the same template as for Table 14.3.2.2.1 for the following tables:

Table 14.3.2.2.1.1

Treatment Emergent Adverse Events (TEAE) by System Organ Class and Preferred Term by CYP2D6 Metabolizer Status
(Safety Analysis Set)

Table 14.3.2.2.1.2

Treatment Emergent Adverse Events (TEAE) by System Organ Class and Preferred Term by BMI Category
(Safety Analysis Set)

Table 14.3.2.2.2

Serious Treatment Emergent Adverse Events (TEAE) by System Organ Class and Preferred Term
(Safety Analysis Set)

Table 14.3.2.2.2.1

Serious Treatment Emergent Adverse Events (TEAE) by System Organ Class and Preferred Term by CYP2D6 Metabolizer Status
(Safety Analysis Set)

Table 14.3.2.2.2.2

Serious Treatment Emergent Adverse Events (TEAE) by System Organ Class and Preferred Term by BMI Category
(Safety Analysis Set)

Table 14.3.2.2.3

Treatment Emergent Adverse Events (TEAE) Resulting in Early Discontinuation by System Organ Class and Preferred Term
(Safety Analysis Set)

Table 14.3.2.2.3.1

Treatment Emergent Adverse Events (TEAE) Resulting in Early Discontinuation by System Organ Class and Preferred Term by
CYP2D6 Metabolizer Status
(Safety Analysis Set)

Table 14.3.2.2.3.2

Treatment Emergent Adverse Events (TEAE) Resulting in Early Discontinuation by System Organ Class and Preferred Term by
BMI Category
(Safety Analysis Set)

Table 14.3.2.3.1
Treatment Emergent Adverse Events (TEAE) in Decreasing Frequency of Preferred Term
(Safety Analysis Set)

Preferred Term	Oliceridine <= 4 mg N=XXX n (%) [E]	Oliceridine >4 to 8 mg N=XXX n (%) [E]	Oliceridine >8 to 16 mg N=XXX n (%) [E]	Oliceridine >16 to 36 mg N=XXX n (%) [E]	Oliceridine >36 mg N=XXX n (%) [E]	All Treated Patients N=XXX n (%) [E]
Patients with at Least 1 TEAE	xxx (xxx.x) [xxx]	xxx (xxx.x) [xxx]	xxx (xxx.x) [xxx]	xxx (xxx.x) [xxx]	xxx (xxx.x) [xxx]	xxx (xxx.x) [xxx]
<Preferred term 1>	xxx (xxx.x) [xxx]	xxx (xxx.x) [xxx]	xxx (xxx.x) [xxx]	xxx (xxx.x) [xxx]	xxx (xxx.x) [xxx]	xxx (xxx.x) [xxx]
<Preferred term 2>	xxx (xxx.x) [xxx]	xxx (xxx.x) [xxx]	xxx (xxx.x) [xxx]	xxx (xxx.x) [xxx]	xxx (xxx.x) [xxx]	xxx (xxx.x) [xxx]
...						
<Preferred term n>	xxx (xxx.x) [xxx]	xxx (xxx.x) [xxx]	xxx (xxx.x) [xxx]	xxx (xxx.x) [xxx]	xxx (xxx.x) [xxx]	xxx (xxx.x) [xxx]

Note: E = Number of events.

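### BMI gets detailed adverse-event tables but is split only at 25, so no pre-specified table shows adverse-event incidence in obese or morbidly obese patients

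*SAP*

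**What the plan says.** SAP 7.7 lists the safety subgroups, ending with "BMI (<25 vs. ≥ 25), and CYP2D6 metabolizer status". Mock Table 14.1.6 carries the same split: under "BMI Group (kg/m2), n" it has rows for <25, ≥25 and missing, and nothing at 30 or 40.

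SAP 8.6.3 gives BMI more weight than most subgroups. Sex, age, race, baseline pain score and initial setting get only the overall summary of treatment-emergent adverse events (TEAEs). BMI and CYP2D6 status also get the detailed tables, which are "displayed by SOC and PT and will be repeated by BMI and CYP2D6 metabolizer status subgroups". The section adds: "These 3 summary tables will also be repeated for serious TEAEs and TEAEs leading to early discontinuation". A table by preferred term alone is repeated for the same two subgroups. The mock displays include, for example, "Treatment Emergent Adverse Events (TEAE) by System Organ Class and Preferred Term by BMI Category". SAP 8.6.2.1 also repeats the exposure summaries by BMI.

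Protocol 3.3.2 has no BMI criterion. It excludes ASA class IV or worse for surgical and medical patients, and ESI score 1 for emergency department patients. The ASA table in Protocol 9.3 gives "obesity (30 < BMI < 40), well-controlled DM/HTN, mild lung disease" among its class II examples and "morbid obesity (BMI ≥40" among its class III examples, both below the exclusion threshold.

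SAP Appendix 1 defines BMI as rounded to one decimal and converts weight by "Weight (kg) = weight (lb) x 0.454".

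**The concern.** The primary objective is safety, and the sponsor singled out BMI for detailed adverse-event review. A single cut at 25 answers only whether patients at or above 25 differ from those below. A patient with BMI 26 and one with BMI 45 fall in the same column, so the planned tables contain no adverse-event rate for obese or morbidly obese patients, although the study may enrol both.

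If either group did have a higher rate, the ≥25 column would average it with the rate in overweight patients. SAP 7.7 lets the sponsor explore subgroup differences that are noticed. A difference that has been averaged away is unlikely to prompt that exploration.

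**Working it through.** There is no plan figure to reproduce. The study is single-arm and descriptive, and Protocol 6.1 and SAP 4.4 give about 1000 patients without a calculation. The check is how far pooling would shrink a raised rate.

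**Inputs.** From the documents: one cut at 25, N about 1000 and five cumulative dose columns (SAP 4.2). Assumed, because the documents give neither: normal BMI with mean 28 or 31 and SD 6 or 7, and an event rate of 10% that doubles to 20% in the higher-risk group.

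**Formula.** Let f be the share of the ≥25 group that carries the raised risk. Then

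pooled rate = 10% × (1 − f) + 20% × f = 10% × (1 + f).

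In general, pooled relative risk = 1 + f × (RR − 1), so the excess shrinks by the factor f.

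| Mean, SD | ≥25 | ≥30 | ≥40 | ≥25 column if risk doubles only at ≥40 | ≥25 column if risk doubles from 30 |
|---|---|---|---|---|---|
| 28, 6 | 69.1% | 36.9% | 2.3% | 10.3% | 15.3% |
| 28, 7 | 66.6% | 38.7% | 4.3% | 10.6% | 15.8% |
| 31, 6 | 84.1% | 56.6% | 6.7% | 10.8% | 16.7% |
| 31, 7 | 80.4% | 55.7% | 9.9% | 11.2% | 16.9% |

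Example, last row: f for ≥40 is 0.0993/0.8043 = 0.123, giving 10% × 1.123 = 11.2%. For ≥30, f is 0.5568/0.8043 = 0.692, giving 16.9%. The <25 column shows 10.0% throughout.

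**Would a ≥30 column be enough?** Not for morbid obesity. The ≥40 share of the ≥30 group runs from 0.0228/0.3694 = 0.062 to 0.0993/0.5568 = 0.178. A ≥30 column would therefore show 10.6–11.8%, hardly better than 10.3–11.2%. The ≥40 group has to be shown on its own.

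**How large is that group?** At 2.3–9.9% of 1000 it is about 23 to 99 patients, or on average 5 to 20 in each of the five dose columns. With no events in the whole group, the one-sided 95% upper bound is 1 − 0.05^(1/n): 12.2% for n = 23 and 3.0% for n = 99.

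**Rounding and conversion.** The exact factor is 0.45359237 kg/lb, and 0.454/0.45359237 = 1.0009. If patients are grouped on the rounded value, the lowest true BMI classed as ≥25 is 24.95/1.0009 = 24.93. Under the same four distributions the band from 24.93 to 25 holds 2.9–4.2 patients per 1000.

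**The case against.** Four points can be made against this, and each limits the claim.

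- **Raised risk.** A reader might infer that obese patients are known to be at higher opioid risk and that the plan hides it. No part of either document says so. The dilution is conditional, and the doubled rate above is only an illustration.
- **The ASA table.** A reader might take Protocol 9.3 as the protocol's own safety stratification by BMI. It is a reproduced society classification, used for eligibility in surgical and medical patients only. Its BMI bands are examples, and it grades physical status rather than opioid risk. What stands is narrower: such patients are not excluded, and 30 and 40 are cut-points the protocol already prints.
- **Recoverable data.** A reader might conclude that the study cannot state incidence in obese patients. It can. BMI is summarised as a continuous variable, Listing 16.2.2.1 gives it by patient, Listing 16.2.5.1 gives adverse events by patient, and SAP 7.7 allows exploration. Only the pre-specified displays lack it.
- **Rounding.** Appendix 1 does not say outright that grouping uses the rounded value, and the effect is trivial. Protocol 3.6.1 lets height be taken by patient attestation in inches. At an assumed 68 inches, one inch moves a BMI of 25 by 25 × ((68/67)² − 1) = 0.75, about ten times the 0.07 at issue.

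Sparse tables are also a fair objection: the ≥40 group is too small to split by dose. That shapes the fix but does not remove the need for one.

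**Conclusion.** The point holds as a gap in pre-specified safety displays. BMI is given detailed adverse-event tables, patients with BMI of 30 and above may enrol, and no planned table shows their adverse-event incidence separately.

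If risk were raised only at ≥40, the ≥25 column would show almost nothing: 10.3–11.2% against 10.0% for a doubled rate. If it were raised from 30 upward, the column would show about 15–17%. The signal would be visible but weakened, and could not be assigned to obesity rather than overweight. These figures rest on an assumed BMI distribution and an assumed doubling. The shrinkage itself follows from the pooling whenever the higher-risk group is only part of the ≥25 group.

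No planned conclusion of the study is invalidated, since all subgroup work is descriptive and untested. This is a cheap improvement worth making before database lock. Rounding is a side note.

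**What to change.** - **SAP 7.7 and mock Table 14.1.6:** replace the single cut with <25, 25 to <30, 30 to <40 and ≥40. The same table already shows age in more than two levels (cuts at 65 and 75).
- **Exposure and overall TEAE summaries repeated by BMI:** use the same four levels.
- **BMI-repeated tables by system organ class and preferred term (all, serious and leading to discontinuation) and by preferred term alone:** use <25, 25 to <30 and ≥30. Add a ≥40 display for the All Treated Patients column only.
- **Minor:** state in Appendix 1 that the cuts apply to unrounded BMI and that rounding is for display.

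Cost: SAP wording and table formats, with no new data, since height and weight are already collected. The <25 group is unchanged and no testing is added. The tables become longer, and the ≥40 group will be small and its rates imprecise, which a table footnote should say.
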